4.0 Study Population and Eligibility

4.1 Inclusion Criteria

- AJCC 8th edition criteria for unresectable stage IIIB, stage IIIC, stage IIID or stage IV melanoma who have received at least 3 months of prior treatment with an anti-PD1 or anti-PDL1 antibody and who have progressed on this treatment. Patients who have received a combination anti-PD1 and anti-CTLA4 therapy who exhibit progression at this interval are also permitted. There are no restrictions regarding time since last anti-PD1 treatment, or number of therapies after anti-PD1.
- Age \geq 18 years;
- ECOG performance status \leq 2 or Karnofsky \geq 60%
- Patients must have normal organ and bone marrow function as defined below:

Lab Test	Criteria
Hemoglobin	\geq 9.0 g/dL
Absolute neutrophil count	\geq 1500 cells/ μ L
Platelets	\geq 100,000 cells/ μ L
Total bilirubin	\leq 1.5 x institutional upper limit of normal (ULN). Patients with Gilbert's syndrome must have normal direct bilirubin
AST/ALT	\leq 2.5x ULN in subjects with liver metastasis, must be within normal limits for those without liver metastasis
Creatinine	$<$ 1.5 mg/dL

- For patients with actionable BRAF mutations, treatment with BRAF and MEK inhibitors prior to initiation on trial is recommended, unless patients are intolerant of therapy or choose not to pursue BRAF targeted therapy.
- Patients must have measurable disease, defined as at least one tumor lesion that can be accurately measured in at least one dimension (longest diameter to be recorded for non-nodal lesions and short axis for nodal lesions) as $\geq 10\text{mm}$ with CT scan, MRI or by calipers if documented on clinical exam. If patients have a single lesion, the lesion must be amenable to biopsy without interfering with radiographic assessment as determined by one of the co-PIs.
- Duvvelisib and nivolumab therapy may be harmful for a developing fetus. Women of child bearing potential (WCBP) must have a negative urine or serum β human chorionic gonadotropin (β hCG) pregnancy test within 7 days before starting treatment. WCBP and men must agree to use highly effective contraception (pharmacologic birth control, barrier methods or abstinence) prior to study entry and for the duration of study participation through 5 months after the last dose of study medication. Should a woman become pregnant while she or her partner are participating in this study, she should inform her treating physician immediately. Men treated or enrolled on this protocol must also agree to use highly effective contraception prior to the study, for the duration of study participation and 12 weeks following the last dose.
- WCBP defined as a sexually mature woman who has not undergone surgical sterilization or who has not been naturally postmenopausal for at least 12 consecutive months for women >55 years of age
- Ability to understand and the willingness to sign a written informed consent document.

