4.2 Exclusion Criteria

4.2.1 Target disease

- Patients with known or suspected CNS metastases are excluded, unless the following criteria are met:
 - Subjects have controlled brain metastasis, defined as metastases without radiographic progression for at least 4 weeks following treatment with stereotactic radiation and/or surgical treatment
 - Subjects must be off steroids without symptoms of CNS disease for at least 2 weeks prior to treatment
 - Subjects with signs or symptoms of brain metastasis are not eligible unless brain metastasis is ruled out by computed tomography or magnetic resonance imaging
- Patients with uveal or mucosal melanoma are excluded

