6.6 Efficacy Evaluations

Efficacy evaluations will be based on tumor response on radiographic imaging, preferably CT scans. Baseline imaging will be obtained within 28 days prior to starting the trial. The same imaging modality will be used for subsequent imaging evaluation. Imaging will be reviewed by investigators for measurements. Measurements will be performed according to RECIST v1.1¹⁹ criteria for size response. Further details on imaging modalities allowed, performing measurements, definition of lesions and evaluation of response are available in section 12.0.

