12.1 Definitions

- **Evaluable for toxicity** – All patients are evaluable for toxicity upon initiating treatment of nivolumab and duvelisib. For the phase I portion, patients should have taken 75% of duvelisib pills according to pill diary and pill counts.
- **Evaluable for objective response** – Patients who have measurable disease at baseline and have their disease re-evaluated at 12 weeks of therapy will be evaluable for response. Patients who

exhibit objective disease progression prior to the end of cycle 1 will also be considered evaluable.

- **Evaluable non-target disease response** – Patients who have baseline lesions that are evaluable but do not meet the definitions of measurable disease have received at least one cycle of therapy and have had their disease re-evaluated will be considered evaluable for non-target disease. The response assessment is based on the presence, absence, or unequivocal progression of the lesions.
- **Measurable disease** – Tumor lesions that can be accurately measured by the longest diameter in the plane of measurement with a minimum size of 10mm by CT scan, 10mm caliper measurement on clinical exam, 20mm by chest x-ray. CT scan thickness should be no greater than 5mm. Tumor measurements must be recorded in mm or decimal fractions of centimeters.
- **Malignant lymph nodes** – To be considered pathologically enlarged and measurable, a lymph node must be $\geq 15\text{mm}$ in short axis when measured by CT scan. Only the short axis will be measured and followed.
- **Non-measurable disease** – All other lesions, including small lesions $< 10\text{mm}$ and lymph nodes $< 15\text{mm}$ are considered non-measurable disease. Other non-measurable disease examples include ascites, pleural or pericardial effusion, lymphangitic involvement of skin or lung, abdominal masses/abdominal organomegaly that don't correlate to CT or MRI, bone lesions, inflammatory breast disease.

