- **Target lesions** – When more than one measurable lesion is present at baseline all lesions up to a maximum of five lesions total (max two per organ) representative of all involved organs should be recorded and measured at baseline. If only 2 organs are involved, the maximum number of target lesions is four. Target lesions should be selected based on lesions with the longest diameter, be representative of involved organs, and should lend themselves to repeated measurements. If lesions do not fulfill these requirements, the next largest lesion that can reproducibly be measured should be selected.

A sum of the diameters (longest for non-nodal lesions, short axis for nodal lesions) for all target lesions will be calculated and reported as the baseline sum of diameters. If lymph nodes are to be included in the sum, then only the short axis will be added. The baseline sum will be used as a reference to further characterize any objective tumor regression in the measurable dimension of the disease.

- **Non-target lesions** – All other lesions or sites of disease including pathological lymph nodes should be identified as non-target lesions and should also be recorded at baseline. Measurements are not required and these lesions should be followed as present, absent or unequivocal progression.

Other considerations

- Lesions that meet radiographic criteria for simple cysts should not be considered malignant lesions, because they are, by definition, simple cysts. Cystic lesions thought to represent cystic metastases can be considered as measurable lesions, if they meet the definition of

measurability described above. However, if non-cystic lesions are present in the same patient, they are preferred for selection as target lesions.

- Lesions situated in a previously irradiated area, or an area subjected to other loco-regional therapy, are usually considered non-measurable unless there has been demonstrated progression in the lesion.

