14.2. Phase II Portion of the Study

The study primary endpoint will be analyzed once the last patient on treatment is on study for 18 weeks.

14.2.1. Study Populations:

Safety population: patients who received any amount of the study regimen.

[figure not shown]
Efficacy population: patients who received at least one cycle of the treatment and at least one efficacy evaluation.

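### Section 4.1 defines measurable disease by size alone, so a patient can be eligible for a response-rate trial with no lesion that section 12.1 counts as measurable

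*Combined protocol and SAP*

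**What the plan says.** Four provisions bear on which lesions count.

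- **Eligibility (4.1).** "Patients must have measurable disease, defined as at least one tumor lesion that can be accurately measured in at least one dimension", at 10 mm or more on CT, MRI or calipers. The same bullet adds a condition: "If patients have a single lesion, the lesion must be amenable to biopsy without interfering with radiographic assessment", as judged by a co-principal investigator. It does not mention earlier radiation, surgery or injection, and has no cross-reference to section 12.
- **CNS exception (4.2.1).** Brain metastases are acceptable if controlled, meaning "metastases without radiographic progression for at least 4 weeks following treatment with stereotactic radiation and/or surgical treatment".
- **Lesion definitions for response (6.6 and 12.1).** Section 6.6 states that the "definition of lesions and evaluation of response are available in section 12.0". Under the other considerations in 12.1, lesions in an irradiated area, or one given other loco-regional therapy, "are usually considered non-measurable unless there has been demonstrated progression in the lesion".
- **Who is counted.** Section 12.1: "Patients who have measurable disease at baseline and have their disease re-evaluated at 12 weeks of therapy will be evaluable for response". The efficacy population in 14.2.1 is wider: "patients who received at least one cycle of the treatment and at least one efficacy evaluation". It does not ask for measurable disease.

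The primary phase II endpoint is the overall response rate (CR plus PR). Section 14.2.2 stops for futility at 0 responses in the first 15 patients and declares efficacy at more than 3 responses in 30 evaluable patients.

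**The concern.** One lesion can satisfy the entry rule and fail the endpoint's own definition. For stereotactically treated brain metastases the two rules pull against each other: 4.2.1 requires that the lesion has not progressed, and progression is the only stated exception in 12.1 that would make it measurable. The same applies to any other irradiated or injected lesion that has stayed quiet.

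The plan expects such patients. Section 3.2.2 lists radiated CNS disease as a subset. Section 4.2.3 bars radiation or surgery only in the 4 weeks before consent. It also allows up to three phase II patients with earlier T-vec, and keeps biopsies away from injected sites without a matching statement about target lesions.

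With a success threshold of four responses, one patient whose response status reflects the lesion rule rather than the drug could change the decision. The error could run either way.

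**Working it through.** **1. The rules side by side, for a patient whose only lesion of at least 10 mm was locally treated and has not progressed since**

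| Rule | Result |
|---|---|
| 4.1, size | Eligible |
| 4.1, single-lesion condition | Applies only if this is the patient's sole lesion; not triggered if there is other, smaller or non-measurable disease |
| 12.1, treated-lesion rule | Usually non-measurable, so no target lesion |
| 12.3.3, table for non-measurable disease | CR is possible; there is no PR category |
| 12.1, evaluable for response | Not evaluable (no measurable disease at baseline) |
| 14.2.1, efficacy population | Included after one cycle and one efficacy evaluation |

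The last two rows disagree on whether the patient is in the response-rate denominator.

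**2. Reproducing the plan's own figures (14.2.2)**

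With a Beta(0.5, 0.5) prior, P(rate > 5%) is 0.890 at 3/30 and 0.968 at 4/30, so at least 4 responses is the right cut for 90%. P(rate < 5%) is 0.695 at 0/10 and 0.789 at 0/15, so the first possible stop is at 15.

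Let p be the true response rate. Then

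P(success) = P(Bin(30, p) ≥ 4) − (1 − p)^15 × P(Bin(15, p) ≥ 4).

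- p = 0.05: 0.0608 − 0.4633 × 0.0055 = 0.058 (plan: below 0.06).
- p = 0.20: 0.8773 − 0.0352 × 0.3518 = 0.865 (plan: over 86%).

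Early stopping is 0.463 at 5% (plan: above 0.46). At 20% it is 0.0352 (plan: below 3.5%), a rounding or simulation difference. The design reproduces.

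**3. One affected patient among the first 15**

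The documents give neither the number of such patients nor their chance of being scored as a responder. I assume one patient and call that chance q. The other 29 respond at rate p.

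- Not scored as a responder: S0 = P(Bin(29, p) ≥ 4) − (1 − p)^14 × P(Bin(15, p) ≥ 4).
- Scored as a responder: S1 = P(Bin(29, p) ≥ 3), because the futility stop at 15 is then avoided.
- Overall: (1 − q) × S0 + q × S1.

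At p = 0.05, S0 = 0.0548 − 0.4877 × 0.0055 = 0.052 and S1 = 0.175.

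| q | P(success) at a true 5% rate |
|---|---|
| no affected patient | 0.058 |
| 0.1 | 0.064 |
| 0.2 | 0.077 |
| 0.3 | 0.089 |
| 0.5 | 0.114 |
| 1 (upper bound) | 0.175 |

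At p = 0.20 with q = 0: S0 = 0.8596 − 0.0440 × 0.3518 = 0.844, against 0.865 with no affected patient.

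**4. Other cases**

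If the patient is instead dropped as not evaluable and not replaced, so that 29 remain with the cut still at 4, power is 0.849. With two affected patients among the first 15, false success is 0.071, 0.098 or 0.128 at q = 0.1, 0.2 or 0.3, and power is 0.820 if neither can respond.

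**The case against.** The best defence is that the plan already contains several safeguards.

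- **The single-lesion condition.** A reader might infer that a patient with nothing but a treated brain metastasis can enroll. That is unlikely, because a lone lesion must be amenable to biopsy without interfering with radiographic assessment. The condition does not close the gap, however. It applies to a single lesion, not a single *measurable* lesion, and a lone irradiated or injected skin or nodal lesion could still pass it.
- **Section 12 governs target selection.** A reader might also infer that meeting 4.1 makes the treated lesion a target. It does not: 6.6 sends lesion definitions to section 12. Inflation therefore needs an investigator to use the latitude in *usually*. That is possible, but nothing in the documents shows it will happen.
- **A false PR is not easy.** It needs a further 30% shrinkage from a baseline scan taken within 28 days before the start, with no new lesions and no non-target progression. This argues for a low q. It does not bring q to zero.
- **Evaluability.** Section 12.1 would call the patient not evaluable, and the success rule speaks of evaluable patients, so the patient need not occupy one of the 30 places. This is a partial answer only, because 14.2.1, the section that defines the analysis population, does not carry the requirement over.
- **CR remains possible** under the non-measurable-disease table, so the power of 0.844 assumes that no such CR occurs.

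**Conclusion.** The point holds as a conflict between the entry rule and the endpoint's definition of measurable disease, made worse by an efficacy population that does not ask for measurable disease. The direction of any effect on the response rate is open: dilution if 12.1 is applied and the patient is kept in the denominator, inflation if *usually* is read loosely.

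Under the assumption of one affected patient among the first 15, false success at 5% moves from 0.058 to between 0.064 and 0.114, above the stated bound of 0.06. If the patient cannot respond, power at 20% falls to about 0.844, below the stated 86%.

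A reader might go further and quote a false-success probability of 0.175, or 0.41 for two patients. Those figures require every affected patient to be a certain false responder, and the documents give no basis for that. They are upper bounds. Nor do the documents show that the response rate *will* be distorted, since they say nothing about how many such patients would enroll. The case for acting is that one entry sentence contradicts the endpoint's definition and is cheap to correct.

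**What to change.** 1. **Section 4.1:** require at least one lesion that is measurable as defined in 12.1, including its rule on irradiated or locally treated lesions. The qualifying lesion must then lie outside any such area (injected sites included) unless its progression after that treatment is documented.
2. **Section 14.2.1:** add measurable disease at baseline to the efficacy population, so that it agrees with the 12.1 definition of evaluable for response. This is settled before treatment, so it does not select patients on outcome.

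Making the treated-lesion rule in 12.1 firm, in place of *usually*, would be a sensible tightening but is secondary. The cross-reference in step 1 would also settle a related mismatch: 4.1 accepts nodes from 10 mm short axis, while 12.1 requires 15 mm.

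**Cost:** a short wording amendment, and a few patients whose only lesion of sufficient size was locally treated become ineligible. The sample size of 30, the futility boundary and the success cut are unchanged, and the planned 0.058 and 0.865 stand.

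### Section 4.1 admits a 10 mm lymph node as measurable disease while 12.1 requires 15 mm on CT, so a node-only patient can be eligible yet have no target lesion for the primary endpoint

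*Combined protocol and SAP*

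**What the plan says.** Section 4.1 makes measurable disease an entry condition and defines it there: "Patients must have measurable disease, defined as at least one tumor lesion that can be accurately measured in at least one dimension", with "longest diameter to be recorded for non-nodal lesions and short axis for nodal lesions". One threshold of at least 10 mm, by CT, MRI or calipers, follows for both lesion types.

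Section 12.1 sets a different rule for nodes. A "lymph node must be $\geq 15\text{mm}$ in short axis when measured by CT scan", and under non-measurable disease it adds that "lymph nodes $< 15\text{mm}$ are considered non-measurable disease". Target lesions are drawn from measurable lesions: "When more than one measurable lesion is present at baseline all lesions up to a maximum of five lesions total" are to be recorded. Evaluability depends on the same term: "Patients who have measurable disease at baseline and have their disease re-evaluated at 12 weeks of therapy will be evaluable for response".

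Section 12.2 adds a third statement. Superficial lesions, with palpable nodes given as an example, are measurable at 10 mm or more by calipers.

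The primary endpoint (3.2.1, 14.2.3.1) is the proportion with a best response of CR or PR. The efficacy population in 14.2.1 requires one treatment cycle and one efficacy evaluation, and does not mention measurable disease. Section 14.2.2 declares efficacy on more than 3 responses in 30 evaluable patients.

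**The concern.** Staff who follow 4.1 to the letter would enrol a patient whose only lesion is, say, a 12 mm node on CT. Section 12 then gives that patient no target lesion. The plan does not settle whether the patient belongs in the response denominator: 12.1 points to exclusion and 14.2.1 to inclusion. Unresectable stage IIIB to IIID disease is eligible and 4.1 provides for patients with a single lesion, so the case is not far-fetched. With 30 patients and efficacy declared at 4 responses, the handling of one or two patients can decide the result.

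**Working it through.** **1. The texts side by side, for a sole node of 10 to under 15 mm short axis on CT**

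| Question | Section | Answer |
|---|---|---|
| Eligible as measurable disease? | 4.1 | Yes |
| Measurable for response? | 12.1 | No |
| Target lesion available? | 12.1 | No |
| PR possible? | 12.3.1; second table in 12.3.3 | No: PR is defined on target lesions, and the non-measurable table has no PR row |
| CR possible? | 12.3.2; second table in 12.3.3 | Yes, if all nodes are below 10 mm and the other non-target conditions are met |
| Evaluable for objective response? | 12.1 | No |
| In the efficacy population? | 14.2.1 | Possibly: measurable disease is not required |

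**2. Direction of bias.** A sole node of d mm must shrink by just over (d − 10)/d to fall below 10 mm: almost nothing at 10 mm, 16.7% at 12 mm, 28.6% at 14 mm. PR needs 30%. Up to 10/0.7 = 14.3 mm the CR route therefore needs less shrinkage than PR does in other patients. Against that, there is no PR category to fall back on, and CR also requires tumor marker normalization. The response rate could move up or down.

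**3. Reproducing the plan's figures.** Inputs from 14.2.2: Beta(0.5, 0.5) prior, 5% reference rate, futility stop at 0 responses in 15, 20 or 25 patients, efficacy if Pr(rate > 5%) is at least 0.90. The posterior is Beta(0.5 + x, 0.5 + n − x).
- Pr(rate > 5%) is 0.890 for 3/30 and 0.968 for 4/30, which confirms the more-than-3 rule.
- Zero responses at 20 or 25 implies zero at 15, so with cut-off r: P(declare) = P(Bin(n, p) ≥ r) − (1 − p)^15 × P(Bin(n − 15, p) ≥ r).
- Power at 20%: 0.8773 − 0.0352 × 0.3518 = 0.865 (plan: over 86%).
- Type I error at 5%: 0.0608 − 0.4633 × 0.0055 = 0.058 (plan: below 0.06).

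**4. Illustration with k affected patients.** k is an assumption. "Kept" columns assume none of the k responds; the others respond at 20%.

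| k | Kept: power, with looks | Excluded: n | 90% rule re-derived: cut-off | Type I error at that cut-off, no looks | Type I error keeping more than 3, no looks |
|---|---|---|---|---|---|
| 1 | 0.849 | 29 | 4 | 0.055 | 0.055 |
| 2 | 0.831 | 28 | 3 | 0.163 | 0.049 |
| 3 | 0.811 | 27 | 3 | 0.151 | 0.044 |
| 4 | 0.788 | 26 | 3 | 0.139 | 0.039 |
| 5 | 0.762 | 25 | 3 | 0.127 | 0.034 |

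For k = 2, kept: 0.8398 − 0.0352 × 0.2527 = 0.831. This places both patients after the futility looks. If both enrol before the first look, that look rests on 13 other patients: 0.8398 − 0.8^13 × 0.3518 = 0.8398 − 0.0550 × 0.3518 = 0.820.

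For k = 2, excluded, with the looks: at cut-off 3, 0.1627 − 0.4633 × 0.0245 = 0.151; keeping more than 3, 0.0491 − 0.4633 × 0.0031 = 0.048. The cut-off moves because Pr(rate > 5%) is 0.908 for 3/28 but 0.899 for 3/29.

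**The case against.** Four points can be made for the plan.

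- **CR remains open.** A reader might infer that these patients can only be non-responders. The documents do not support that, because 12.3.2 and the second table in 12.3.3 allow CR through non-target disease. This stands. The power figures that assume no response from them are one illustration, not the expected effect.
- **The type I error of about 0.16 is not a property of the node threshold.** A reader might infer that the mismatch nearly triples the error rate. That requires at least two exclusions and a cut-off re-derived at the smaller n. Two patients lost for any other reason would do the same, and 14.2.2 states the cut-off as more than 3 in 30 evaluable patients. Kept at more than 3, the error is about 0.05. This stands too.
- **Existing safeguards.** Section 4.1 has a co-PI judge single lesions, and 6.6 refers to section 12.0 for lesion definitions. Neither resolves the conflict. The co-PI check asks whether a biopsy would interfere with radiographic assessment, not whether the node is large enough. The reference in 6.6 concerns efficacy evaluation, while 4.1 carries its own definition.
- **Section 12.2 supports 10 mm for palpable nodes.** This is correct for caliper measurement, so the conflict is cleanest for nodes measured on CT. It also conflicts with the unconditional under-15 mm entry in 12.1, so it adds a passage to reconcile.

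**Conclusion.** The contradiction between 4.1 and 12.1 is certain and lies in current text. An eligible patient can have no target lesion, no route to PR, and an undefined place in the primary analysis. How much this matters depends on a number the plan does not give. With two such patients and no responses from them, power at 20% is 0.82 to 0.83 instead of 0.865, depending on when they enrol. If they are excluded, type I error is about 0.05 or about 0.15 to 0.16, according to whether the cut-off is kept or re-derived. With one exclusion the cut-off stays at 4. Because non-target CR is possible, and is reached with little shrinkage for nodes near 10 mm, bias could run in either direction. The finding supports correcting the definitions; it does not show that the sample size or decision rule is wrong.

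**What to change.** In 4.1, require nodes measured by CT or MRI to be at least 15 mm in short axis, in line with 12.1, and keep 10 mm for non-nodal lesions. In the same amendment, reconcile the 10 mm caliper wording for palpable nodes in 4.1 and 12.2 with the under-15 mm entry in 12.1, so that one definition of a measurable node applies throughout. For any patient already enrolled without a target lesion, state whether 12.1 or 14.2.1 governs the response denominator.

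The cost is a short text amendment to a few definitions, with no change to sample size or decision rule. The downside is that a few patients whose only disease is a node of 10 to 14 mm become ineligible.
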